### 5.4.2 Adverse Events

An AE is defined as any untoward medical occurrence in a patient or clinical investigation patient, temporally associated with the use of a medicinal product, whether or not considered related to the medicinal product. All AEs that occur from the first dose of study treatment through 35 (±5) days after the last dose of study treatment is administered will be recorded on the AE CRF. From the time the study Informed Consent is signed through the first dose of study drug administration, only serious AEs (SAEs) that are related to study procedures will be recorded.

AEs will be coded using the Medical Dictionary of Regulatory Activities (MedDRA, Version 18.0) and will be classified by MedDRA system organ class (SOC) and preferred term (PT). All AEs will be classified for severity by the Investigator according to the definitions set forth by the Common Terminology Criteria for Adverse Events (CTCAE Version 4.03).

All AE tables will be presented with number and percentage of patients. AE listings will include patient ID, gender, age, race, AE verbatim term and preferred term, AE start date and end date,

AE duration, CTCAE grade, if the AE is SAE or not, relation to study drug, study drug action, outcome, and if treatment is given.

Only treatment-emergent AEs (TEAE), as defined in Section 5.4.2.2, will be summarized in tables. SAEs reported prior to treatment but after informed consent will only be provided in AE listings.

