- Pruritus (83%, 92%, 0%)
- Palmar-plantar erythrodysesthesia syndrome (33%, 58%, 0%)
- Decreased appetite (17%, 42%, 100%)
- Rhinorrhea (33%, 75%, 33%)
- Paronychia (67%, 25%, 33%)

Many of these most commonly reported treatment-related AEs in the 24-mg/day cohorts were also reported at an incidence of  $\geq 50\%$  incidence in **NOV120101-202** (16 mg/day continuous), ie, diarrhea (95%), stomatitis (59%), rash (77%), pruritus (64%), and paronychia (54%).

The most commonly reported Grade 3 TEAEs ( $\geq 25\%$  incidence in any 24-mg/day cohort) in **HM-PHI-101** (2 cohorts, 24 mg/day and 24 mg/day) and **HM-PHI-102** (1 cohort) were as follows:

- Diarrhea (33%, 25%, 33%)
- Nausea (0%, 8%, 33%)
- Decreased appetite (0%, 8%, 33%)
- Hemoglobin decreased (0%, 0%, 33%)

Different from the most commonly reported Grade 3 TEAEs in the 24-mg/day cohorts, Grade 3 TEAEs reported at an incidence of  $\geq 25\%$  in **NOV120101-202** (16-mg/day continuous dosing) were rash (59%) and mucosal inflammation (26%). Refer to poziotinib IB for complete details.

**Table 1 Most Common Treatment-Emergent Adverse Events ( $\geq 30\%$  in Group Total for each Study) in Descending Order by Preferred Term (Safety Population) - Phase 1 and Phase 2 Completed Studies with Poziotinib (Doses  $\geq 12$  mg/day)**

Preferred Term	Number (%) Patients		
	HM-PHI-101 a N=55	HM-PHI-102 a N=20	NOV120101-202 N=39
Any Adverse Event	55 (100)	20 (100)	39 (100)
Diarrhea	48 (87)	20 (100)	36 (92)
Rash	47 (86)	13 (65)	30 (77)
Stomatitis	42 (76)	16 (80)	23 (59)
Decreased Appetite	34 (62)	13 (65)	21 (54)

Preferred Term	Number (%) Patients		
	HM-PHI-101 a N=55	HM-PHI-102 a N=20	NOV120101-202 N=39
Paronychia	13 (24)	13 (65)	21 (54)
Pruritus	33 (60)	11 (55)	25 (64)
Mucosal Inflammation	13 (24)	6 (30)	18 (46)
Rhinorrhea	17 (31)	8 (40)	4 (10)
Dry skin	6 (11)	6 (30)	15 (38)
Fatigue	21 (38)	3 (15)	15 (38)
PPE Syndrome	18 (33)	3 (15)	3 (8)
Acne	18 (33)	0	0
Vomiting	16 (29)	6 (30)	4 (10)
Dermatitis Acneiform	2 (4)	6 (30)	5 (13)

PPE = palmar-plantar erythrodysesthesia syndrome.

(a) Includes all patients and all doses.

Note: Adverse events are listed by decreasing order of highest percent in any study.

MedDRA version: 14.0 was used for Studies **HM-PHI-101** and **HM-PHI-102**; MedDRA version 17.0 was used for **NOV120101-202**.

Source: Poziotinib IB Table 9.

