#### **Cohort 3 - only if Cohort 2 is stopped due to toxicity:**

- Rate of Grade 3 or greater AEs of special interest (ie, diarrhea, skin rash, stomatitis) are identified during Safety Data Review after the first 6 patients and again after 12 patients have completed **Cycle 1**:
  - **>33%:** End enrollment in **Cohort 3**
  - **$\leq 33\%$ :** Keep enrolling **Cohort 3** until 20 patients are enrolled and treated

Toxicity will be assessed based on the grade of the adverse events using CTCAE version 4.03.

[figure not shown]
All treatments will be taken orally, once daily (QD) at approximately the same time each morning. On **Day 1** of each cycle, the patient's absolute neutrophil count (ANC) must be

$\geq 1.0 \times 10^9/L$  and platelet count must be  $\geq 100 \times 10^9/L$  before administering poziotinib. For **Cycle 1** and **Cycle 2** only, the ANC and platelet count should also be confirmed prior to the dose on **Day 8**. **Day 1** of a new cycle is equivalent to **Day 22** of the previous cycle, with a window of  $\pm 3$  days for the visit. If a visit is delayed during 1 cycle, then all subsequent cycles will be delayed sequentially.

All patients will be treated until disease progression, death, intolerable adverse events, or up to a maximum of 24 months, whichever comes first.

The study design diagram is presented in **Figure 2**, and the Schedule of Study Assessments and Procedures is presented [Appendix 1](#).

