### 8.6 Safety Analysis

The overall incidence of treatment-emergent AEs (TEAE) (ie, AEs occurring from the time the first dose of the study drug until 35 ( $\pm 5$ ) days after the last dose) and the proportion of patients who discontinue because of a TEAE are the primary safety outcome measures. The number and percent of patients with new-onset TEAEs will be summarized by the MedDRA (version 17) system-organ-class (SOC) level and Preferred Term for all treated patients, for each cohort. The summary of TEAEs will be presented in the following categories:

- Number and percentage of patients with any TEAEs by SOC and Preferred Term.
- Number and percentage of patients with any SAEs by SOC and Preferred Term.
- Number and percentage of patients with related TEAEs by SOC and Preferred Term.
- Number and percentage of patients with TEAEs causing discontinuation of the study by Body System and Preferred Term.

In addition, the number and percent of patients with TEAEs by grade will be summarized. Adverse events reported prior to treatment but after IC will be provided in a listing.

Finally, the number of completed cycles will also be summarized and analyzed descriptively.

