## 2 OBJECTIVES

### 2.1 Primary Objective

- To establish the dosing schedule for poziotinib to be used in the clinical development program
- To evaluate the Objective Response Rate (ORR) of poziotinib in patients with human epidermal growth factor receptor 2 (HER2)-positive MBC

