#### **5.4.2.2 Treatment Emergent Adverse Events**

TEAEs are AEs that occur from the first dose of study treatment until 35 ( $\pm 5$ ) days after the last dose of study treatment. If it cannot be determined whether an AE is treatment-emergent (based on start date or, if the start date is missing then based on the stop date), then the AE will be considered treatment-emergent.

Summary of TEAEs by MedDRA SOC and PT will be presented in a separate table with any grade and with Grade 3 or 4. Patients who experience more than one type of AE will be counted under each of the corresponding PTs. Patients who experience different episodes of the same AE will be counted only once under the corresponding PT. Similarly, for determination of MedDRA SOC incidences, patients who experience multiple AEs under the same SOC will be counted only once for that SOC. Listing of all TEAEs will also be provided.

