#### **5.4.2.7 Adverse Events of Special Interest**

Summary of TEAEs, treatment-related AEs, and SAEs for diarrhea, rash, stomatitis, and pneumonitis by MedDRA PT will be provided in separate tables with any grade and with Grade 3 or 4. Study day of first incidence for diarrhea, rash, and stomatitis will be summarized using median and range. Rash of special interest will be reported as collective of multiple PTs related to rash, including rash, dermatitis acneiform, rash maculo-papular, etc. Similarly, stomatitis of special interest will be reported as collective of multiple PTs related to stomatitis, including stomatitis and mucosal inflammation.

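### Toxicity is reported by cohort only as any-time percentages over unequal time on drug; a fixed-time incidence by cohort should be added

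*SAP*

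**What the plan says.** SAP 2.1 gives as the first primary objective: "To establish the dosing schedule for poziotinib to be used in the clinical development program". The two schedules studied are 24 mg for two weeks of three (Cohort 1, 33 enrolled) and 16 mg continuously (Cohort 2, 34 enrolled); see SAP Section 3.

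On toxicity, SAP 5.4.2 says "All AE tables will be presented with number and percentage of patients", and SAP 5.4 reports safety for each cohort. The counting rule in SAP 5.4.2.2 is "Patients who experience different episodes of the same AE will be counted only once under the corresponding PT". The window is set there too: "TEAEs are AEs that occur from the first dose of study treatment until 35" (±5) days after the last dose. Protocol 3.1 sets treatment duration: "All patients will be treated until disease progression, death, intolerable adverse events, or up to a maximum of 24 months".

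Three other elements bear on timing:
- SAP 5.4.1 summarizes exposure: duration, cycles, days dosed, relative dose intensity, and the study day of first dose reduction and first interruption.
- SAP 5.4.2.7 adds an onset summary: "Study day of first incidence for diarrhea, rash, and stomatitis will be summarized using median and range".
- The Safety Data Review (Protocol 3.1, SAP Section 3) looks at Grade 3 or greater diarrhea, rash and stomatitis once the first 6, and then 12, patients of Cohort 2 have finished Cycle 1. The protocol has the same review for Cohort 3, which was never opened.

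Protocol 8.6 states that overall TEAE incidence and "the proportion of patients who discontinue because of a TEAE are the primary safety outcome measures".

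**The concern.** An any-time percentage has a fixed denominator but a time at risk that differs between patients and possibly between cohorts. A cohort that stays on drug longer has more opportunity to record a first event. Two schedules with the same risk per unit of time can then show different percentages, and the confidence interval does not reveal it.

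Unequal exposure is plausible here. The SAP's summary of changes says the lower-dose cohorts were added because the original dose was poorly tolerated, and Protocol 1.2 gives better tolerability as the aim. If that aim is met, fewer Cohort 2 patients stop early. What is at stake is the descriptive reading of tolerability behind the first primary objective. There is no between-cohort test, so no error rate is affected.

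**Working it through.** The plan states no figure on this point, so there is none to reproduce. Taken from the documents: the window ending 35 days after last dose, the 21-day cycle, the 24-month cap, and 33 and 34 patients. Assumed: hazards and time on drug.

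**1. Any-time percentage, constant hazard.** Let h be the hazard of a first event per cycle, with time on drug exponential with mean m cycles. The tail is 35/21 = 1.667 cycles. Ignoring the 24-month cap and letting the hazard continue through the tail:

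percentage = 1 − exp(−1.667h) / (1 + hm)

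With h = 0.10, exp(−0.1667) = 0.8465.
- m = 3: 1 − 0.8465/1.3 = 34.9%
- m = 6: 1 − 0.8465/1.6 = 47.1%

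The gap is 12.2 points with no true difference. If instead the hazard fell to zero at last dose, the percentage is h/(h + 1/m): 23.1% and 37.5%, a gap of 14.4 points.

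**2. Second scenario, with the 24-month cap.** Cycle 1 incidence is 10%, so λ = −ln(0.9)/(21/30.4375) = 0.153 per month. Time on drug is exponential with median 2 or 4 months, capped at 24, plus the 35-day tail.

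| Hazard after Cycle 1 | Median 2 months | Median 4 months | Gap (points) |
|---|---|---|---|
| Unchanged | 41.8% | 55.4% | 13.6 |
| 25% of Cycle 1 hazard | 20.3% | 27.4% | 7.1 |
| 10% of Cycle 1 hazard | 14.4% | 17.8% | 3.4 |

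In the first row a simulation of 400,000 patients per setting gives about 0.153 first events per patient-month and 10% in Cycle 1 for both medians. At constant hazard the gap is 11.3 points (24.4% vs 35.7%) for 5% Cycle 1 incidence and 11.6 points (64.3% vs 75.9%) for 20%.

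**3. Fixed-time incidence, inputs of step 1.**
- Events counted whether or not drug has stopped, hazard unchanged after stopping: 1 − exp(−0.10) = 9.5% at Day 21 and 1 − exp(−0.20) = 18.1% at Day 42, in both cohorts.
- Stopping drug as a competing event: [h/(h + 1/m)] × [1 − exp(−(h + 1/m)t)]. Day 21 (t = 1): 8.1% vs 8.8%. Day 42 (t = 2): 13.4% vs 15.5%. An exposure effect of about 1 to 2 points remains. The same figures arise under the first convention if the hazard falls to zero once drug stops.

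**4. Is the data window long enough?** A patient whose only dose is on Day 1 is followed for AEs to Day 36, or Day 31 at the short end of the ±5 days, so Day 21 is covered. Day 42 is covered if the last dose is on Day 7 or later (42 − 35), or Day 12 at the short end (42 − 30). Protocol 4.3 brings the End-of-Treatment Visit forward if new treatment starts, so some early leavers may need censoring.

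**5. Sampling error.** For 12 of 33 patients the exact 95% interval is 20% to 55%, about ±17 points.

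**6. What the existing elements supply.** The exposure summary shows whether time on drug differs, but not AE incidence at a common time. The median onset day is defined only among patients with the event and has no at-risk denominator. The Safety Data Review does use a fixed window, but it governs enrollment into the later cohorts and was not specified for Cohort 1.

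**The case against.** The strongest reply has four parts.
- The size is assumed. The documents give no time on drug and no hazard by cohort, and Protocol 1.2 expects acute diarrhea. With mainly early onset the gap is only 3 to 7 points in the second scenario, well inside sampling error. This stands. The same section, however, calls rash and stomatitis more chronic, so early onset cannot be assumed for every event.
- Exposure is tabulated by cohort, so a careful reader would see an imbalance. True, but that reader could not convert it into an incidence at a common time.
- The study is non-randomized and descriptive, and the only written toxicity rule already uses Cycle 1. True; but that rule does not compare the two schedules.
- Graded tables are planned, so the plan does not rest on any-AE incidence. Also true.

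Three stronger readings are tempting and not supported. A reader might infer that the tables can reverse the tolerability ranking. The illustration sets the hazards equal, so there is no ranking to reverse. With step 1 inputs, reversal would need the shorter-treated cohort's true hazard to exceed the other's by a ratio below about 1.54, and nothing in the documents places it there. A reader might infer that the schedule will be chosen on any-time percentages; no passage says so. And since Protocol Table 1 shows any AE in 55/55, 20/20 and 39/39 patients, a reader might want overall TEAE incidence replaced. Two of those studies include all doses, and the graded tables carry the finer information, so replacement is not needed.

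**Conclusion.** The point holds as a gap in the safety reporting. Every AE table is an any-time percentage over a window that lengthens with time on drug, and nothing in the plan gives AE incidence by cohort at a common time. If time on drug differs, the longer-treated cohort shows a higher percentage at the same hazard.

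At constant hazard with time on drug doubled, the artefact is roughly 11 to 14 points. It is 3 to 7 points with 10% Cycle 1 incidence and onset mainly in that cycle. It vanishes if exposure is equal or no first events occur after the early period. These sizes rest on assumed hazards and exponential time on drug; which cohort is affected cannot be stated from the documents. The artefact is no larger than the sampling error of about ±17 points per cohort, but it is systematic. The change is a cheap, worthwhile improvement and does not put the planned tables in error.

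**What to change.** In SAP 5.4.2.7 add, by cohort in the Safety Analysis Population, the cumulative incidence with 95% CI of first Grade 3 or greater diarrhea, rash or stomatitis at Day 21 and Day 42, using the grouped terms already defined there, with the curve as a figure.

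State the convention. Preferably count events inside these windows whether or not the patient has stopped drug, with death as the competing event (Aalen-Johansen) and censoring where AE collection ends earlier. If stopping drug is treated as a competing event instead, say so and note that a small exposure effect of about 1 to 2 points remains under the assumptions above.

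Add one sentence: any descriptive comparison of the schedules' tolerability rests on these fixed-time figures read together with the SAP 5.4.1 exposure summary. Keep the any-time tables and the protocol's stated safety measures.

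The cost is one table and one figure from AE and dosing dates already collected. The intervals will be wide with 33 and 34 patients, and the text should say so.

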#### **5.4.2.1 Overall Summary**

An overall summary table of TEAEs will be provided. The summary will include any TEAE, TEAE by severity, any treatment-related AE, treatment-related AE by severity, SAEs, and AEs leading to study drug discontinuation.

#### **5.4.2.2 Treatment Emergent Adverse Events**

TEAEs are AEs that occur from the first dose of study treatment until 35 ( $\pm 5$ ) days after the last dose of study treatment. If it cannot be determined whether an AE is treatment-emergent (based on start date or, if the start date is missing then based on the stop date), then the AE will be considered treatment-emergent.

Summary of TEAEs by MedDRA SOC and PT will be presented in a separate table with any grade and with Grade 3 or 4. Patients who experience more than one type of AE will be counted under each of the corresponding PTs. Patients who experience different episodes of the same AE will be counted only once under the corresponding PT. Similarly, for determination of MedDRA SOC incidences, patients who experience multiple AEs under the same SOC will be counted only once for that SOC. Listing of all TEAEs will also be provided.

#### **5.4.2.3 Treatment-Related Adverse Events**

Assessment of relatedness to study drug for all AEs will be classified by investigators and reported. "Definitely related", "probably related" and "possibly related" AEs will be considered as treatment related. An AE will be assigned as treatment-related if the relationship to study drug is missing.

The incidences of treatment-related AEs will be presented by MedDRA SOC and PT with any grade and with Grade 3 or 4.

#### **5.4.2.4 Serious Adverse Events**

SAEs are defined (21 CFR 312.32, ICH of Technical Requirements for Registration of Pharmaceuticals for Human Use E2A Guideline) as those AEs that meet any of the following criteria:

- Results in death.

- Is life-threatening: ie, any event that, in the opinion of the Investigator, poses an immediate risk of death from that event.
- Requires inpatient hospitalization or prolongation of existing hospitalization (excluding hospitalizations for study therapy, disease-related procedures, or placement of an indwelling catheter, unless associated with other SAEs).
- Results in a persistent or significant disability/incapacity.
- Results in a congenital anomaly/birth defect.
- Includes important medical events that may not be immediately life threatening or result in death or hospitalization but may jeopardize the patient or may require intervention to prevent one of the outcomes listed in this definition.

Listing of all SAEs will be provided. Treatment-emergent SAEs and treatment-related SAEs will be summarized by MedDRA SOC and PT with any grade and with Grade 3 or 4.

#### **5.4.2.5 Maximum Severity of Adverse Events**

TEAEs and treatment-related AEs will be summarized by MedDRA SOC, PT, and maximum CTCAE severity grade. AEs with a missing severity grade will not be included in these analyses. Patients who experience the same event at more than one severity level will be counted only once under the maximum severity level. The overall adverse event incidences will also be presented in these tables as a reference.

#### **5.4.2.6 Other Important Adverse Events**

AEs leading to death and study drug discontinuation will be presented in separate listings and the incidence will be summarized in the overall summary of TEAE table.

#### **5.4.2.7 Adverse Events of Special Interest**

Summary of TEAEs, treatment-related AEs, and SAEs for diarrhea, rash, stomatitis, and pneumonitis by MedDRA PT will be provided in separate tables with any grade and with Grade 3 or 4. Study day of first incidence for diarrhea, rash, and stomatitis will be summarized using median and range. Rash of special interest will be reported as collective of multiple PTs related to rash, including rash, dermatitis acneiform, rash maculo-papular, etc. Similarly, stomatitis of special interest will be reported as collective of multiple PTs related to stomatitis, including stomatitis and mucosal inflammation.

#### **5.4.3 Laboratory Parameters**

Clinical laboratory samples will be collected at screening and throughout the study. The clinical laboratory values will be classified according to the NCI CTCAE Version 4.03. Tables of shifts in severity and in clinical abnormality from baseline to worst post-baseline on study, for key laboratory parameters, will be provided.

**5.4.4 Vital Sign Data**

A summary of raw values and changes from baseline values will be provided at each scheduled time point for the following measurements: body temperature, systolic and diastolic blood pressure, and heart rate. A listing of all values will also be included.

**5.4.5 ECOG Performance Status**

Descriptive statistics will be presented for ECOG scores at baseline. The number and percentage of patients with shifts from baseline ECOG score (0, 1, or 2) to the worst post-baseline ECOG score (0, 1, 2, 3, or 4) will be summarized.

**5.4.6 Cardiac Assessment**

Cardiac assessment will be provided in the data listings.

